8.4 Routine Adverse Event Reporting

All Adverse Events **must** be reported in routine study data submissions.

Adverse event data collection and reporting, which are required as part of every clinical trial, are done to ensure the safety of patients enrolled in the studies as well as those who will enroll in future studies using similar agents. AEs are reported in a routine manner at scheduled times during the trial.

8.5 Secondary Malignancy

A secondary malignancy is a cancer caused by treatment for a previous malignancy (*e.g.*, treatment with investigational agent/intervention, radiation or chemotherapy). A secondary malignancy is not considered a metastasis of the initial neoplasm.

All secondary malignancies that occur following treatment with the trial agent should be reported expeditiously. Three options are available to describe the event:

- **8.5.1** Leukemia secondary to oncology chemotherapy (*e.g.*, acute myelogenous leukemia [AML])
- **8.5.2** Myelodysplastic syndrome (MDS)
- **8.5.3** Treatment-related secondary malignancy

Any malignancy possibly related to cancer treatment (including AML/MDS) should also be reported via the routine reporting mechanisms outlined in each protocol.

9. PHARMACEUTICAL INFORMATION

A list of the adverse events and potential risks associated with the investigational or commercial agents administered in this study can be found in Section 7.1.

9.1. Olaparib

Chemical Name: 4-[(3-{[4-(cyclopropylcarbonyl)piperazin-1-yl]carbonyl}-4-fluorophenyl)methyl]phthalazin-1(2H)-one

Other Names: Lynparza[®]

Classification: Olaparib is a small molecule antineoplastic poly (ADP-ribose) polymerase (PARP) enzyme inhibitor, including PARP1, PARP2, and PARP3.

Mechanism of Action: PARP enzymes are involved in DNA transcription, cell cycle regulation, and DNA repair. Olaparib is a potent oral PARP inhibitor that induces synthetic lethality in BRCA1/2 deficient tumor cells through the formation of double-stranded DNA breaks which cannot be accurately repaired, which leads to disruption of cellular homeostasis and cell death

CAS Registry Number: 763113-22-0

Approximate Solubility: Olaparib is a crystalline solid, is non-chiral and shows pH-independent low solubility across the physiological pH range.

9.1.1. Olaparib Tablets

How Supplied: Olaparib tablets are supplied by AstraZeneca Pharmaceuticals LP. Olaparib tablets for oral administration contain 100 mg or 150 mg of olaparib. Inactive ingredients in the tablet core are copovidone, mannitol, colloidal silicon dioxide and sodium stearyl fumarate. The tablet coating consists of hypromellose, polyethylene glycol 400, titanium dioxide, ferric oxide yellow and ferrosoferric oxide (150 mg tablet only).

150 mg tablets: green to green/grey, oval, bi-convex, film-coated tablet, with debossment 'OP150' on one side and plain on the reverse, are available in:

- Bottles of 60 tablets (NDC 0310-0679-60) and
- Bottles of 120 tablets (NDC 0310-0679-12).

100 mg tablets: yellow to dark yellow, oval, bi-convex, film-coated tablet, with debossment 'OP100'on one side and plain on the reverse, are available in:

- Bottles of 60 tablets (NDC 0310-0668-60) and
- Bottles of 120 tablets (NDC 0310-0668-12).

Storage: Store at 20°C to 25°C (68°F to 77°F), excursions permitted to 15°C to 30°C (59°F to 86°F). Store in original bottle to protect from moisture. Once the bottle is opened, olaparib tablets must be used within 3 months of the opening date; unused tablets should be discarded. Instruct patients not to open a bottle until they are ready to use it.

Stability: Stability data from three production scale batches stored in the proposed packaging under long term conditions for up to 36 months (25° C / 60° RH) and under accelerated conditions (40° C / 75° RH) for 6 months according to the ICH guidelines has been provided. The 36 month data show no significant change with regards to the description, assay, organic impurities, polymorphic form, water content or particles size distribution for the samples stored at 25° C/60% RH, nor after 6 months at 40° C/75% RH and 6 months at 50° C/ambient humidity. Based on the available stability data, the proposed retest period of 48 months for olaparib when stored in LDPE bags at or below 30° C was considered acceptable.

Route of Administration: Oral administration per the protocol treatment schedule.

Method of Administration: Inform patients that olaparib should be taken twice daily with or without food. Instruct patients that if they miss a dose, they should take their next normal dose at the usual time. Swallow each tablet whole. Do not chew, crush, dissolve, or divide tablet. Do not take more than 4 tablets daily. Inform patients to avoid grapefruit, grapefruit juice, Seville oranges, Seville orange juice, pomelos, and starfruit while taking olaparib as these food products can alter the metabolism of olaparib. Inform patients not to substitute olaparib tablets (100 mg and 150 mg) with olaparib capsules (50 mg) on a milligram-to-milligram basis due to differences in the dosing and bioavailability of each formulation.

10. BIOMARKER, CORRELATIVE, AND SPECIAL STUDIES

With the exception of patients who withdraw due to toxicity or withdraw consent, patients on this trial will ultimately develop PARP inhibitor resistant disease. This represents an important opportunity to collect biospecimens to evaluate resistance mechanisms and create patient derived xenograft tumor models for therapeutic development.

10.1 Integrated Laboratory Studies – Exploratory Objective

- 10.1.1 Tissue collection is optional. If the patient consents, archival tissue will be obtained from previous surgical resection. If the patient undergoes biopsy at the time of disease progression at part of standard of care practice, tissue will be requested from this biopsy as well.
- 10.1.2 Specimen Collection: **Pretreatment** tumor samples will be obtained from archived formalin-fixed, paraffin embedded (FFPE) tissue from the Pitt Biospecimen Core (PBC). Subject samples will undergo pathologic review with to ensure accurate diagnosis and tissue quality, >50% tumor and >50% viable cells, for subsequent molecular analysis. **Post-treatment** samples will be obtained at the time of detected disease recurrence or progression. A portion of each biopsy will undergo pathologic review as above.
- 10.1.3 Research Specimens: All specimens will be de-identified and clinical information stored in a locked computer database system. Research samples will be processed in the [name] lab. If tissue is limited, samples will be snap frozen in liquid nitrogen and stored at -80°C for DNA/RNA isolation (QIAGEN® AllPrep DNA/RNA kit). For larger specimens (laparoscopic biopsy/resection), a portion of each sample will be (1) snap-frozen for RNA and DNA isolation, (2) disaggregated into single cells suspensions and live cell suspensions frozen, and (3) immediately transferred in DMEM media to Champions Oncology for PDX development.
- 10.1.4 Characterize genomic changes associated with olaparib resistance: For samples with limited tissue and therefore not amenable to PDX formation, we will use BROCA analysis (http://tests.labmed.washington.edu/BROCA#BROCA_Gene_List) on both pre and post-olaparib treatment samples to evaluate 69 different genes associated with HR defects. A total of 1.4 Mb are sequenced and the average coverage ranges from 320 to >1,000 sequencing reads per bp. Genomic regions are captured using biotinylated RNA oliognucleotides (SureSelect), prepared in paired-end libraries with ~200 bp insert size, and sequenced on an Illumina HiSeq2000. For samples for which PDX models are generated, we will perform whole genome sequencing (WGS) on the primary tissue, then compare WGS of primary tumors and PDX tumors. For specific genes in which we find molecular alterations, we will use knockdown and rescue assays in cell lines to validate olaparib resistance related to the identified target.
- 10.1.5 Characterize transcriptome changes associated with olaparib resistance: For an unbiased evaluation of mRNA expression changes associated with olaparib resistance, we will perform RNASeq (Novogene, utilizing Illumina's NovaSeq platform) with a random-primed cDNA synthesis non-strand-specific protocol. RNASeq will be compared between pre and post-olaparib treatment samples. Candidate drivers of resistance will be compared with BROCA results and then validated with knockin/knockout studies as above. Resistance mechanisms identified in the above studies can then be used in future work with the PDX models to test novel therapeutics to overcome PARP-I resistance.
- 10.1.6 Pharmacokinetics: To explore exposure-response relationships between olaparib

exposure and toxicity/efficacy. A steady-state trough sample will be obtained around day 28. Trough concentrations (if need be corrected for time since dosing) will be compared between patients with/without response and patients with/without toxicity. This assay will be performed at the UPMC Hillman Cancer Center Cancer Pharmacokineitc and Pharmacodynamics Facility. (CPPF). The published olaparib assay has successfully been implemented and is available (Nijenhuis et al. Journal of Chromatography B, 940 (2013) 121–125). Note: plan the patient's day 28 visit such that their blood can be drawn at about the time they would otherwise take their dose, but **BEFORE** they take it. Ask patients to take bring their olaparib so they can take their dose after their PK blood draw. See appendix D for practical details.

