6.1. Agent Administration

Olaparib treatment will be started when CA125 rises by two-fold of their nadir value. Olaparib will be dosed at 300 mg orally twice a day. Twenty-eight days of treatment will be considered one cycle. Patients will be required to maintain a medication diary (See Appendix B).

Patients starting olaparib will continue treatment until disease progression, per RECIST v1.1³⁹ or intolerable toxicity, defined as any grade 3 or 4 adverse event, per National Cancer Institute's Common Terminology Criteria for Adverse Events (CTCAE) v5.0 or Patient Reported Outcomes-Common Terminology Criteria for Adverse Events (PRO-CTCAE), that does not resolve completely or to grade 1 within 28 days after onset. Patients removed from study for unacceptable adverse event(s) will be followed closely until resolution or stabilization of the adverse event (at least 30 days).

Olaparib is FDA-approved for maintenance therapy for patients with platinum sensitive recurrent epithelial ovarian cancer with a complete or partial response to most recent platinum based chemotherapy. Therefore, drug will be covered by standard insurance. Additionally, after discussion with The UPMC Health Plan, they will approve treatment after 2 prior lines even with the delay in standard start time defined by the maintenance indication.

Treatment will be administered on an outpatient basis. Appropriate dose modifications are described in Section 7. No other investigational or commercial agents or therapies may be administered with the intent to treat the patient's malignancy.

Reported adverse events and potential risks are described in Section 7.

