6.2.2. Supportive care

No routine prophylactic medications are indicated at the start of therapy. In general, the use of any concomitant medication/therapies deemed necessary for the care of the patient are allowed with the exceptions noted in 6.2.1

6.3. **Duration of Therapy**

Patients will be enrolled continuously to the study. Patients will continue evaluation and treatment until one of the following criteria applies:

- Disease progression per RECIST v1.1³⁹
- Unacceptable adverse event(s) defined as any grade 3 or 4 adverse event, per National Cancer Institute's Common Terminology Criteria for Adverse Events (CTCAE) v5.0 or PRO-CTCAE, that does not resolve to grade ≤ 1 within 28 days after onset.
 - Treatment will be interrupted for any grade 3 or 4 event related to treatment. If the toxicity resolves entirely or to grade 1, treatment will be restarted with a dose reduction. If the event does not resolve within 4 weeks or if two previous treatment interruptions with subsequent dose reductions occur, the patient will be withdrawn.
- Patient withdraws consent.
- Development of second malignancy (except for basal cell carcinoma or squamous cell carcinoma of the skin) that requires treatment, which would interfere with this study.
- Intercurrent illness that prevents further administration of treatment
- General or specific changes in the patient's condition render the patient unacceptable for further treatment in the judgment of the investigator.

6.4. **Duration of Follow Up**

Patients will be followed until the initiation of the next therapy post olaparib treatment. Each patient, regardless of reason for removal from study, will have at least 18 months follow up relative to time of enrollment. Secondary efficacy endpoints will be tracked after official follow-up has been completed.

Assessments in follow up:

- Office visit or review of medical records every 3 months
- Survival endpoints both progression free survival (PFS) and overall survival (OS)

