7.2.7. Renal Impairment

CrCl 51 to 80 mL/minute: No dosage adjustment necessary; monitor closely for toxicity, as an increase in mean AUC has been observed in patients with mild impairment.

CrCl 31 to 50 mL/minute: Reduce dose to 200 mg twice daily.

 $CrCl \leq 30 \text{ mL/minute}$: There are no dosage adjustments provided in the manufacturer's labeling (has not been studied).

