- H. Financial toxicity will be measured through a) monetary measure using the Modified Collection of Indirect and Nonmedical Direct Costs (COIN) (See Appendix I), b) objective measure of financial burden assessed using Barrera et al.'s Economic Hardship questionnaire (See Appendix J), and c) subjective measure of financial distress will be gauged using the Comprehensive Score for Financial Toxicity (COST Measure) (See Appendix K).
- I. Pregnancy test for women of childbearing potential (WOCBP) must be done within 24 hours prior to initiation of olaparib.
- J. Tissue collection is not mandatory. If permission granted, tissue prior to initiation on olaparib will be obtained from archival stores. If patient undergoes biopsy at the time of progression as part of standard of care, tissue will be collected after routine processing.
- K. A mandatory trough plasma sample will be obtained only once at approximately 28 days after initiation of treatment (See **Appendix L**).
- L. BRCA testing required (Results not needed for registration
- M. Chart review or office visit every 3 months for 18 months from time of enrollment

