13.3.5 Analysis of Patient Reported Outcomes, Quality of Life and Financial Toxicity Endpoints

Additional **Secondary Endpoints** include a series of quality of life instruments and financial toxicity measures. These instruments will be administered starting at onset of trial enrollment and periodically thereafter. Patient reported adverse events, worry and distress (3 instruments measured every 4 weeks), health related quality of life, physical functioning and financial toxicity (5 instruments measured every 12 weeks) will provide data for longitudinal analysis with mixed effects linear models. We will focus on change over time particularly between the two treatment periods, pre and post olaparib. Our linear mixed effects models will emphasize random coefficients that allow non-linear profiles, typically polynomial regression, restricted cubic splines or piecewise linear splines with a knot to represent the time of starting olaparib. These models will permit us to estimate whether quality of life and financial toxicity change over the course of the clinical trial and, in particular, whether the observed change suggests a shift that is consistent with the start of olaparib therapy.

For drug exposure measured through quantitating olaparib by LC-MS/MS in a trough sample, trough concentrations between groups will be compared with non-parametric Wilcoxon signed rank test with significance set at P<0.05. If significant, we may explore ROC analyses.

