APPENDIX L: PHARMACOKINETICS SHEET DAY 28 - OLAPARIB

Phase IIA trial of delayed initi	ation of olaparib maintenance	e therapy in platinum sensitive recurr	ent ovarian cancer				
Study Sample Collection Log							
Subject Initials: (First_Middle_Last)		Subject ID:	Date:	BSA: (m²)	Site Name:		
Pharmacokinetic (PK) Sample	Collection						
At approximately Day 28, right before the patient would otherwise take their dose, ~3-4 mL of peripheral blood will be collected in a purple top tube (e.g. BD vacutainer 367861 plastic 13 x 75 4 mL tube); Invert tube to mix; centrifuge for 10 min at ~1000 x g; aspirate plasma and place into appropriately-labeled microcentrifuge tubes. After processing, store plasma at -70°C or below. At the time of sample transfer, a copy of this completed PK form must be transferred also. Note the times administering of oral dose, in this form; specifically the time of previous dose, and the time of the dose immediately after the blood draw.							
		Olaparib					
Protocol Sample and Time Point	Projected Sample Due Time (24 hr clock)	Actual Time (24 hr clock)		Commer	nts		
Day ~28 Administer the olaparib after taking the blood sample Olaparib Dose (mg):							
Time of previous olaparib dose				commonly the	night prior		
pre/trough blood sample							
Time of olaparib dose immediately after sample

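### The day-28 trough comparison by toxicity can be biased downwards, because toxicity before the sample can interrupt or lower the dose and the plan sets no rule for it

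*Combined protocol and SAP*

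**What the plan says.** Objective 1.2.10 is to explore how olaparib exposure relates to toxicity and efficacy. Footnote K of the study calendar (section 11) sets the exposure measure: "A mandatory trough plasma sample will be obtained only once at approximately 28 days after initiation of treatment". Section 10.1.6 gives the comparison: troughs "will be compared between patients with/without response and patients with/without toxicity". The one correction it names, where needed, is for time since dosing. Section 13.3.5 gives the test: "trough concentrations between groups will be compared with non-parametric Wilcoxon signed rank test with significance set at P<0.05". It names no covariate, dose adjustment or exclusion. Section 13.3.3 tabulates each patient's worst grade in each toxicity category and does not relate onset to the sample.

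The dosing sections link toxicity to exposure. The starting dose is fixed in 6.1: "Olaparib will be dosed at 300 mg orally twice a day". Section 6.3 states "Treatment will be interrupted for any grade 3 or 4 event related to treatment", with restart at a lower dose after recovery. The haematologic tables in section 7 step down to 250 mg and then 200 mg twice daily. Sections 7.2.1 to 7.2.5 interrupt for uncontrolled nausea or vomiting, fatigue, dysgeusia, diarrhoea and constipation. The Appendix L sheet records the dose ("Olaparib Dose (mg") and the time of the previous dose, but no analysis text uses the dose.

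**The concern.** An exposure–toxicity analysis asks whether higher exposure leads to toxicity. Here part of the toxicity can come before the exposure measurement and change it. A patient with a related grade 3 event in week 2 may be off drug, or back on a lower dose, when the trough is drawn. Her low trough is then a result of the toxicity, yet she counts in the toxicity group. The planned comparison could show lower exposure with toxicity where there is no relation, or shrink a real positive one.

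At stake is a listed secondary objective tested at P<0.05. Section 13.3.5 allows ROC analyses after a significant result, and a trough cut-off found this way could mislead later work.

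**Working it through.** The plan gives no power, effect size or sample size for this comparison, so there is no stated figure to reproduce. The size of the bias was explored by simulation.

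**Inputs from the documents.** 75 evaluable patients (13.2); starting dose 300 mg; reduced doses 250 mg (250/300 = 0.83) and 200 mg (200/300 = 0.67); significance level 0.05.

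**Assumptions not in the documents.** 40% of patients have toxicity (30 with, 45 without); lognormal trough with CV 50% or 80%, so the log-scale SD is √ln(1 + CV²) = 0.47 or 0.70; a trough during interruption is 2% of its usual value; the shares interrupted or reduced are varied. A two-sided Mann–Whitney test was used because the groups are independent. That 13.3.5 names the signed rank test, which is for paired data, is a separate point.

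**Check 1: no true relation, 30 versus 45, about 4,000 runs per cell** (simulation error up to about one percentage point).

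| Share of toxicity group off drug / on 250 mg | Rejection, all samples kept | Rejection, off-drug samples dropped |
|---|---|---|
| 0% / 0% | 5% | 5% |
| 0% / 20% | 5–6% | not applicable |
| 3% / 10% | 6–7% | 5–6% |
| 5% / 10% | 8–9% | 5% |
| 10% / 20% | 16–17% | 5–6% |
| 20% / 20% | 40–45% | 5–6% |
| 30% / 20% | 68–71% | 5–7% |

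With 30 patients in the toxicity group, 10% is three patients and 20% is six. From 10% upwards nearly all rejections point to lower trough with toxicity. The median trough ratio (toxicity/no toxicity) is 0.86–0.90 at 10%/20% and 0.76–0.82 at 20%/20%. With off-drug samples dropped it is 0.95–0.97 in both cells.

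**Check 2: a true positive relation, 400,000 patients per scenario.** Toxicity was drawn from a logistic model on the trough at 300 mg, with a stated odds ratio (OR) per SD of log trough. A share of the toxicity group then had its trough changed. Median ratios:

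| Scenario | True ratio | 25% at 250 mg | 25% at 200 mg | 25% off drug | 50% at 200 mg |
|---|---|---|---|---|---|
| OR 1.5, CV 50% | 1.20 | 1.15 | 1.09 | 0.98 | 0.98 |
| OR 1.5, CV 80% | 1.32 | 1.26 | 1.19 | 0.98 | 1.08 |
| OR 2.0, CV 50% | 1.34 | 1.29 | 1.22 | 1.11 | 1.10 |

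Every shift is downwards. The ratio falls below 1 at about 25% off drug when the OR is 1.5, and at about 50% on 200 mg when the OR is 1.5 and the CV 50%. A stronger relation needs larger shares. In these scenarios reduction to 250 mg weakens the relation without reversing it.

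**Check 3: effect of dividing every trough by dose.** Section 6.2.1 lowers the dose to 100 mg with a strong CYP3A inhibitor, and 7.2.7 states "CrCl 31 to 50 mL/minute: Reduce dose to 200 mg twice daily". Normalising to 300 mg would multiply those troughs by 300/100 = 3 and 300/200 = 1.5. The result would no longer be the exposure these patients had.

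**The case against.** The strongest reply is that an off-drug sample is not what the plan describes. Section 10.1.6 calls for a steady-state trough, drawn just before a dose that is then taken, and Appendix L has a field for that dose. An interrupted patient has neither a steady state nor a next dose. With those samples dropped, rejection returns to 5–7%. This stands as to size: almost all the bias comes from off-drug samples. It does not close the gap, because no exclusion rule is written, the sample is labelled mandatory, and the choice decides the result.

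The shares may also be small. Scheduled blood counts fall on day 1 of each cycle, so much haematologic toxicity would first be seen at about the time of the draw. Section 7.1 lets treatment-related anaemia be managed by transfusion without interruption. Grade 1 events, and grade 2 anaemia or neutropenia, need no dose change. Being on 250 mg at the draw requires onset, recovery and restart within about 28 days. All of this is fair, and the small-share rows of the table reflect it. Symptomatic events are the likelier early route: section 8.1 lists nausea at 58–77% and fatigue at up to 67%, without timing.

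A reader might infer that the CYP3A-inhibitor and renal dose reductions add to the bias. The documents do not support that. Those reductions are not responses to toxicity on study, and the measured trough already reflects the dose taken.

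Finally, counting only later toxicity discards early events, which may be the ones most closely tied to exposure at the starting dose. That is a real cost, and the reason to keep the all-toxicity analysis alongside.

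**Conclusion.** The point holds as a possible downward bias in one secondary comparison. The mechanism follows from the text: toxicity can alter the trough before it is drawn, and neither a toxicity onset window nor a rule for interrupted patients prevents this. The size is conditional on the share off drug at the draw. Under the assumptions above, false-positive rejection is about 6–8% at 3–5%, 16–17% at 10% and 40–45% at 20%.

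A reader might go further and infer that the relation is certainly biased, or reversed. The documents do not give the share of patients modified before day 28, so neither can be claimed. Where a true positive relation exists, reversal needs about 25% or more of the toxicity group off drug, or about 50% or more at 200 mg, and more than that if the relation is strong. The change is worth making because the analysis text can settle the matter before data are seen. The objective is exploratory in wording, and the primary endpoint is unaffected.

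**What to change.** Amend 10.1.6 and 13.3.5 only; no dosing rule or data collection changes.

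- **Samples.** Exclude from the trough comparison any sample taken while olaparib is interrupted, identified from the previous-dose time and dose on the Appendix L sheet. Report how many are excluded from each group.
- **Main comparison.** Compare troughs by toxicity that begins after the sample. Leave out patients whose toxicity began earlier; do not count them as free of toxicity.
- **Sensitivity analysis.** Repeat with all toxicity. Here only, rescale the trough of a patient whose dose was lowered for toxicity to the dose at onset: trough × (dose at onset ÷ dose at sampling), for example × 300/250 = 1.2. This assumes that trough is proportional to dose, which should be stated.
- **No general dose-normalisation.** Leave troughs after CYP3A-inhibitor or renal dose changes as measured.

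The cost is fewer patients and events in this comparison, and a main result that describes only patients still taking olaparib at day 28.
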